## 6.7 Cataracts

Cataracts were observed in toxicology studies of eltrombopag in rodents. Routine monitoring of patients for cataracts is recommended. In controlled studies in thrombocytopenic patients with HCV receiving interferon based therapy (n = 1439), progression of pre-existing baseline cataract(s) or incident cataracts was reported in 8 % of the eltrombopag group and 5 % of the placebo group. Screening ophthalmic assessments will be performed in those patients who complain of new or recent onset of visual symptoms or visual impairment at the time of AML diagnosis or those with known prior or existing ocular conditions. Ocular conditions that will need baseline evaluation include any vitreoretinal diseases, age-related macular degeneration, optic nerve disease, glaucoma and corneal diseases as well as patients in whom cataracts are clinically suspected. In those cases, a detailed ocular examination will be performed by an ophthalmologist and will include check for refractive errors, slit-lamp examination of anterior ocular structures, slit-lamp biomicroscopy of posterior pole and indirect ophthalmoscopy. Subsequent assessments including follow up exams will be performed if clinically indicated. For patients developing ocular symptoms during eltrombopag therapy, a detailed assessment will be carried out as mentioned earlier and will be documented as adverse effect. The baseline ophthalmic assessments where indicated needs to be completed prior to administration of the study drug.

## 6.8 Risk of QT/QTc Prolongation

There is no indication of a QT/QTc prolonging effect of eltrombopag at doses up to 150 mg daily for 5 days. The effects of PROMACTA at doses up to 150 mg daily for 5 days on the QT/QTc interval was evaluated in a double-blind, randomized, placebo- and positive-controlled (moxifloxacin 400 mg, single oral dose) crossover trial in healthy adult subjects. Assay sensitivity was confirmed by significant QTc prolongation by moxifloxacin. A 12-lead ECG will be obtained for each patient at screening (baseline). A pre- and post-dose 12-lead ECG will be performed. The post-dose ECG is to be performed within a 2-4 hour window post-dose (preferably within 3 hours after administration of study medication). If assessment cannot be

performed at 3 hours post-dose, record actual time of ECG performed. Thereafter, ECG will be performed if clinically indicated.

## 7.0. TREATMENT PLAN

### 7.1. Eltrombopag Administration

Consecutive eligible patients will receive eltrombopag at an initial oral dose of 200 mg once daily. For patients of East-Asian heritage (Japanese, Chinese, Thai, Taiwanese and Korean), the starting dose will be 100 mg orally once a day.

### 7.2. Dose Rationale

Eltrombopag 200 mg once daily has been selected as the starting dose for this study (100 mg for subjects of East Asian heritage). The maximum dose of study medication is 300 mg once daily (150 mg in subjects of East Asian heritage). The rationale for allowing dose titration up to 300 mg once daily is based on the following considerations:

- The effective dose for eltrombopag for AML patients with chemotherapy-induced thrombocytopenia is unknown, and 300 mg is the maximum dose that is currently being considered in the eltrombopag clinical program, as described in the CIB.(11)
- In a placebo-controlled Phase II study (NCT00102726) in 183 cancer patients receiving carboplatin and paclitaxel, eltrombopag was dosed at 50 mg, 75 mg and 100 mg with placebo as control arm in 1:1:1:1 ratio ) for 10 days after carboplatin and paclitaxel administration for up to 8 cycles. Eltrombopag was generally well tolerated as described in the CIB. (11). The study results for the 100 mg group demonstrated that there was evidence for increased platelet production in all three treatment arms after the nadir, with a gradual rise in platelet counts from Day 8 to 18 of chemotherapy. No apparent safety issues at 100 mg were identified.(28)
- In a Phase II, non-randomized, open label pilot study of eltrombopag in aplastic anemia patients treated with immunosuppressive therapy and with refractory thrombocytopenia (NCT00922883), no observed toxicities were reported in this study to date with intrasubject dose escalation of eltrombopag starting at 50 mg and going up to 150 mg.(29) The higher dose was continued in an extension phase. Improvements of both platelet and erythrocyte values have been observed following eltrombopag exposure in these patients.
- In ITP subjects, a dose exposure and response relationship has been seen for eltrombopag doses of 30 mg to 75 mg once daily. There was no significant difference between the safety profile of ITP subjects receiving 30, 50 or 75 mg of eltrombopag when administered for up to 6 weeks.
- In HCV subjects, a dose, exposure and response relationship has been seen for eltrombopag doses of 30 mg to 75 mg once daily, with geometric mean AUC (0- $\tau$ )

approximately 2-fold higher than that observed in ITP patients at the same dose. There was no significant difference between the safety profile of HCV subjects receiving 30, 50 or 75 mg of eltrombopag, and the frequency of adverse events in these subjects did not increase in a dose-dependent manner. Two Phase III studies have recently completed (TPL103922/ENABLE 1 and TPL108390/ENABLE 2) in subjects with HCV-related thrombocytopenia and led to its FDA approval in November of 2012. The pooled data from these studies demonstrates that eltrombopag treatment increased platelet counts in thrombocytopenic subjects with HCV infection to a level sufficient to allow initiation and maintenance of antiviral therapy for subjects who would otherwise be ineligible or poor candidates for peginterferon-based antiviral therapy. Such antiviral therapy plus eltrombopag enabled 21% of patients to achieve a sustained viral response (SVR) rate; 13% of subjects in the control arm (which also included eltrombopag during the OL Phase of the study) achieved an SVR. The results were statistically significant.

- In vitro, there is a clear relationship between the eltrombopag concentration and the anti-proliferative effect of eltrombopag on leukemic cells.(11-13) Based on preliminary PK from Part 1 of this study, it is expected that doses of 200 to 300 mg eltrombopag will result in plasma concentrations at or above the in vitro IC50 values demonstrating anti-leukemic effects in preclinical experiments for the majority of the eltrombopag dosing interval.
- In healthy subjects, a clear dose, exposure and response relationship has been seen for eltrombopag doses of 10 mg to 200 mg administered once daily for 5 days. Eltrombopag was well tolerated in healthy subjects at all dose levels. A starting dose of 100 mg once daily eltrombopag (50mg for East Asians) has been studied in 46 subjects with chemotherapy-induced thrombocytopenia. No apparent safety issues at 100 mg were identified.
- Based on the PK in subjects with chemotherapy-induced thrombocytopenia (solid tumors), and anticipating similar PK in patients with hematologic malignancies, the predicted exposure in subjects with MDS or AML receiving 300 mg eltrombopag is expected to average 358 ug.h/mL at steady-state (typical 50 year old male subject), with significant intersubject variability. This is similar to the exposure observed in patients with HCV receiving 75 mg eltrombopag. Covariates of exposures are gender, age, and East Asian Heritage. Scaling the exposure of subjects with solid tumors enrolled in the 100 mg dose group to a dose of 300 mg results in an average exposure of 513 $\mu$  g.h/mL, 51% higher than the exposure observed in patients with HCV receiving 75 mg eltrombopag.
- Preliminary results of a Phase II, multicenter, prospective, placebo-controlled, single blind study of eltrombopag (EQoL-MDS) administered at a 50 mg initial daily initial dose with increased every 2 weeks in low and intermediate-1 risk adult MDS patients with PLT count <30 Gi/L suggest safety of eltrombopag in terms of drug-related adverse events and disease progression. In such patients, eltrombopag treatment is effective in raising PLT counts and in reducing the risk of bleeding and is associated with significant improvements in quality of life.(30)

- There is evidence that higher doses of growth factors are required in subjects with cancer: the effective erythropoietin (EPO) dose in MDS is several times higher than the doses used in renal anemia.(1,14,16, 31-34) Anticipating impaired absorption and bioavailability of orally administered eltrombopag in AML patients resulting from mucositis of the gastro-intestinal tract, an often observed side effect of intensive remission IC, we plan to administer higher doses than have been utilized in other non-oncologic settings.
- To ensure subject safety, the current study uses a dose escalation scheme in which subjects are exposed to the lowest dose necessary to achieve the desired platelet count target. Only subjects who have tolerated the previous dose and have not yet benefited from study medication will be considered for the next highest dose, dependent on platelet counts. This approach minimizes potential risks while allowing the subject the maximum potential for benefit.
- Modified dosing for subjects of East Asian heritage has been implemented for the following reasons. In healthy Japanese subjects, plasma eltrombopag AUC (0- $\tau$ ) was approximately 80% higher when compared to non-Japanese healthy subjects who were predominantly White. Similarly, in patients with ITP, plasma eltrombopag exposure was approximately 70% higher in East Asian subjects as compared to non-East Asian subjects who were predominantly White.
- There are limited data on the use of eltrombopag in patients aged 65 years and older. In the clinical studies of eltrombopag, overall no clinically significant differences in safety of eltrombopag were observed between subjects aged at least 65 years and younger.

### 7.3 Dose Adjustments for Eltrombopag

If after 2 weeks, the platelet count fails to reach 50,000/ $\mu$  L or above, the dose will be increased to 300 mg orally daily (150 mg orally daily for East-Asians). Depending on tolerability, dose modification will be individualized based on the patient's platelet count response according to the following rules:

Dose Modification / Adjustment of Eltrombopag	
If platelet count is $\leq$ 50,000/ $\mu$ L after 2 weeks of treatment with starting dose of eltrombopag*	Increase daily dose to 150 mg for East-Asians and 300 mg for all other ethnicities
If platelet counts are between 50,000 and $<$ 100,000/ $\mu$ L (untransfused) on the starting or escalated dose of eltrombopag	Continue on the same dose
If platelet counts reach $\geq$ 100,000/ $\mu$ L (untransfused) on the starting or escalated dose of eltrombopag at any time on study	Discontinue eltrombopag

\* Starting dose will be 100 mg for East-Asians and 200 mg for other ethnicities.

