### **1.3 Thrombocytopenia**

Thrombocytopenia is a common problem in patients with acute leukemia and other hematologic malignancies treated with intensive chemotherapy. The current standard treatment strategy to prevent or manage thrombocytopenia-associated bleeding complications relies exclusively on supportive platelet transfusions. However, this therapeutic approach is expensive, time consuming and associated with risks of alloimmunization and bloodstream infections. Moreover, the effects of platelet transfusions last only for 3-7 days.(17) The incidence of alloimmunization to platelets range from 9-50 % (18,19) and in these patients, platelet transfusions are ineffective in raising platelet counts. Although use of leukoreduced products has reduced the risk of alloimmunization, it still remains at about 4 %. (18) Other immune-mediated problems include febrile reactions and transfusion-related acute lung injury (TRALI). The reported incidence of febrile reaction ranges from 0.13 to 37.5 % per unit in hematology/oncology patients.(20) The incidence of TRALI in patients receiving high-volume plasma products including apheresed platelets has been reported to range from 1 in 1,300 to 1 in 5,000 transfusions.(21-23) In addition, there remains a risk of infections from platelet transfusions. Estimated residual risk of acquiring Hepatitis C Virus (HCV) and Human Immunodeficiency Virus (HIV) from donations from repeat donors (after nucleic acid testing) is 1 per 1,935,000 and 1 per 2,135,000, respectively.(24) The chance of acquiring Hepatitis B virus infection is approximately 1 in 200,000. The risk of bacterial transmission is approximately 1 in 50,000 apheresis platelets.(25, 26)

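### In Section 7.3 the lead sentence and the three dose rows do not share one platelet count or one boundary at 50,000/µL, so some week-2 patients meet no row and others get conflicting instructions

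*Combined protocol and SAP*

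**What the plan says.** Section 7.3 states the escalation rule twice. The lead sentence applies "If after 2 weeks, the platelet count fails to reach 50,000"/µL or above. The first table row applies to counts at or below 50,000/µL "after 2 weeks of treatment with starting dose of eltrombopag". Neither mentions transfusion.

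The other two rows do. The continue row covers 50,000 to under 100,000/µL and carries the condition "untransfused) on the starting or escalated dose of eltrombopag". The discontinue row covers 100,000/µL and above and carries "untransfused) on the starting or escalated dose of eltrombopag at any time on study". Section 7.3 does not define untransfused.

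The purpose of escalation is in Section 7.2: "Only subjects who have tolerated the previous dose and have not yet benefited from study medication will be considered for the next highest dose". Sections 4.1 and 5.10.6 allow supportive transfusion throughout, under institutional practice. Section 8.2 requires every platelet transfusion on eltrombopag to be documented with its date.

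**The concern.** A dose table should place each patient in exactly one row at the decision time. This one does not, for two reasons: its rows do not all refer to the same kind of platelet count, and its stated boundaries disagree at 50,000/µL.

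Transfusion is routine in these patients, and those still thrombocytopenic after two weeks on the drug are the ones the escalation step addresses. If a transfusion has lifted the count above 50,000/µL on the day it is read, the table gives no instruction and the lead sentence points away from an increase. The dose would then depend on the timing of a transfusion or on individual judgement. Two patients with the same response to the drug could receive different doses, and secondary recovery times observed after week 2 would mix those doses.

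**Working it through.** The plan states no figure to reproduce here; the check is of the rule's logic and timing.

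**Step 1: apply each rule literally at two weeks on the starting dose.** Inputs are the lead sentence and three rows of Section 7.3.

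| Count (/µL) | Transfusion status | Table rows met | Lead sentence |
|---|---|---|---|
| Below 50,000 | Untransfused | Increase | Increase |
| Exactly 50,000 | Untransfused | Increase, and continue if that range includes its lower end | No increase |
| Above 50,000, under 100,000 | Untransfused | Continue | No increase |
| 100,000 or more | Untransfused | Discontinue | No increase |
| Below 50,000 | Transfused | Increase | Increase |
| Exactly 50,000 | Transfused | Increase | No increase |
| Above 50,000, under 100,000 | Transfused | None | No increase |
| 100,000 or more | Transfused | None | No increase |

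There are two faults. A transfused count above 50,000/µL meets no row. A count of exactly 50,000/µL gets opposite answers from the table and the lead sentence and, if untransfused, can fall in two rows.

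**Step 2: test the obvious repair.** If the untransfused condition were added to the increase row and nothing else changed, all four transfused lines above would meet no row, instead of two. The missing word in that row is therefore not the whole fault. The rows and the sentence need a common basis.

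**Step 3: place the decision in time.** Induction chemotherapy (IC) runs over days 1–7.

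- Section 4.1 puts a gap of 7–9 days after IC: first dose on day 7 + 7 = 14 to 7 + 9 = 16. The two-week decision falls on day 14 + 14 = 28 to 16 + 14 = 30.
- Section 4.1 also allows five business days from a day 14–17 marrow. Taking five business days as seven calendar days, the latest start is day 17 + 7 = 24 and the latest decision is day 24 + 14 = 38.

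The earliest decision is day 28 on either reading. The primary endpoint (Sections 10.1.1 and 12.0) closes at day 24, which is 28 − 24 = 4 days sooner.

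**Step 4: bound the delay.** Treatment lasts 28 days (Section 7.7), so 28 − 14 = 14 days remain at the decision. Section 1.3 says "the effects of platelet transfusions last only for 3-7 days". Section 8.2 requires a blood count daily in hospital, within 72 hours of discharge, then weekly. Section 7.3 sets no single-day window, so a later count at or below 50,000/µL still meets the increase row. Assuming the count falls back once one transfusion wears off, the delay is up to about 7 days, leaving about 14 − 7 = 7 days at the escalated dose. Repeated transfusions that keep the count above 50,000/µL could extend the delay to all 14 days.

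**The case against.** The strongest reply is that a sensible clinician would read the table as intended. Section 7.2 refers to benefit from study medication, Section 7.3 speaks of individualised adjustment, and recorded transfusion dates allow the status of any count to be recovered. Section 10.2 even has a working transfusion-free definition, five consecutive days at or above 50,000/µL without a platelet transfusion. This limits the practical harm but does not remove the conflict. Section 7.2 gives no rule for transfused counts, the individualised adjustment in 7.3 is expressly tied to the tabled rules, and 7.3 does not invoke the 10.2 definition.

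The other limits stand. A transfused patient at or below 50,000/µL meets the increase row. A reader might infer that anyone transfused within about a week of the decision is exposed; the table does not support that, and the documents give no transfusion trigger or increment from which to estimate the share. Nor is half the course necessarily lost, since a later count can trigger the increase.

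A reader might also infer that response classification in Section 10.1.2 changes, because partial and no response refer to the highest or maximal escalated dose. That cannot be shown. No response there requires 8 weeks of therapy in a 4-week course. The highest-dose route to partial response requires that dose for the whole study, although escalation follows two weeks on the starting dose. Read literally, neither can be met whether or not the patient is escalated. Those are separate faults.

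**Conclusion.** The point holds in limited form. Section 7.3 conflicts with itself: it leaves transfused week-2 counts above 50,000/µL without a row, and it gives incompatible instructions at exactly 50,000/µL. No other section resolves either case.

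Only patients lifted above 50,000/µL by a transfusion, or at exactly that value, are affected. Their number cannot be derived from the documents. The consequence may be no more than a delayed increase, up to about 7 of the remaining 14 days after a single transfusion under the assumption stated above.

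The tempting stronger conclusion, that the main result is at risk, is not supported: escalation comes at least 4 days after the day-24 endpoint, so that endpoint and the two-stage decision built on it are unaffected. What may be affected is consistency of dosing after week 2 and the secondary recovery times reached after that point. This rests on a literal reading of the rows and on IC occupying days 1–7.

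**What to change.** The sponsor should reconcile the lead sentence and all three rows of Section 7.3 so that they use one stated transfusion status for the platelet count and one boundary at 50,000/µL, and so that every week-2 patient falls in exactly one row. Changing the increase row alone would not achieve this. The section should also state what untransfused means for this purpose. Both that definition and the dosing rule itself are for the sponsor to choose.

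The cost is a short wording amendment, with the Novartis and ethics approvals that Section 13.0 requires for any change. The transfusion dates collected under Section 8.2 are enough to apply the rule, so no new case report form field, visit or test is needed.

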#### 7.4 Dose delays, modifications or discontinuation for non-hematologic side effects

**7.4.1 Infection:** Subjects who experience an infection requiring intravenous antibiotics will not have eltrombopag discontinued. If the subject experiences infection severe enough to require vasopressors or intubation, the drug will be withheld until the patient is stable.

**7.4.2 Liver function abnormalities:** In the event of an increase in the ALT level to  $\geq 3$  times the ULN in patients with normal liver function or  $\geq 3X$  baseline in patients with elevations in transaminases before treatment, eltrombopag will be discontinued until ALT is  $\leq 2.5$  times the ULN or from baseline. For all patients (whether on starting dose or escalated dose prior to discontinuation), eltrombopag will be restarted at the starting dose. Eltrombopag will be discontinued permanently if the toxicity reappeared on the starting dose. Other criteria for permanent discontinuation of eltrombopag will be if ALT levels increase ( $\geq 3$  times the ULN in patients with normal liver function or  $\geq 3X$  baseline in patients with elevations in transaminases before treatment) and are:

- progressive, or
- persistent for  $\geq 1$  week, or
- accompanied by increased direct bilirubin, or
- accompanied by clinical symptoms of liver injury or evidence for hepatic decompensation

**7.4.3 Cardiac arrhythmia:** Onset of new onset arrhythmias during treatment with eltrombopag that can be adequately managed will not be a reason for discontinuation of eltrombopag. In patients with normal baseline QTc intervals (prior to starting eltrombopag), a QTc prolongation of  $\geq 500$  milliseconds (ms) will be a reason for temporarily discontinuing eltrombopag only if no other secondary etiology (electrolyte abnormalities or other concomitantly administered QTc prolonging drugs) could be identified and corrected. If QTc prolongation of  $> 500$  ms is clinically attributed to eltrombopag, then EKG should be checked daily till QTc returns to baseline and eltrombopag can be resumed at the discontinued dose. If QTc  $> 500$  ms occurs following reintroduction of eltrombopag, then eltrombopag should be permanently discontinued.

**7.4.5 Renal impairment:** No dose adjustments or discontinuation of eltrombopag is necessary in patients who develop acute kidney injury (with or without hemodialysis support) during remission IC or while on eltrombopag.

#### 7.5 Dose delays, modifications or discontinuation for hematologic side effects

**7.5.1 Thrombosis/Embolism:** Subjects who experience a deep venous thrombosis (excluding line-related thrombus) or a pulmonary embolus, a TIA or stroke, or a myocardial infarction at any time while on eltrombopag will discontinue the drug and go off study. Patients with platelet counts of  $> 50,000/\mu\text{l}$  at the time of thrombosis will be treated with enoxaparin or another appropriate anticoagulant as clinically indicated. They will be treated for the thrombotic event as otherwise clinically-indicated.

**7.5.2 Peripheral blood abnormalities:** The development of significant worsening of anemia or neutropenia while on study will require discontinuation of eltrombopag and additional evaluation including a bone marrow biopsy as clinically indicated.

